3.3.2 Transition from Schedule 1, *Monitoring ATI* to Schedule 3, *Follow-up on ART*

For participants on Schedule 1, *Monitoring ATI*, any of the following non-virologic criteria will trigger ART re-initiation and transition to Schedule 3, *Follow-up on ART*:

- Confirmed CD4+ T-cell count < 350 cells/mm³ (ie, on 2 consecutive samples)
- Any HIV-related syndrome (eg, ARS, an opportunistic infection)
- Pregnancy or breastfeeding
- ART re-initiation requested by participant
- ART re-initiation requested by primary HIV care provider or clinical research site (CRS) Investigator of Record (IoR) (eg, if deemed medically necessary)

A confirmatory sample should be drawn at the next visit (within approximately 1-2 weeks) following the first CD4+ T-cell count < 350 cells/mm³ (see HVTN 805/HPTN 093 SSP for details).

3.3.3 Transition from Schedule 2, *ATI monitoring with viremia*, to Schedule 3, *Follow-up on ART*

For participants on Schedule 2, *Monitoring ATI with viremia*, the following virologic criteria will trigger ART re-initiation and transition to Schedule 3, *Follow-up on ART*.

From the Week 0 visit to the Week 24 visit in Schedule 2:

- Viral load remains $\geq 1,000$ copies/mL for ≥ 4 consecutive weeks AND viral load has not dropped 0.5 log from the previous week

This ART re-initiation criterion applies irrespective of missed visits and must take account of VL results $\geq 1,000$ copies/mL experienced by a participant while on Schedule 1. Furthermore, assessing whether participants meet this criterion may require additional visits beyond those scheduled from Week 8 (Visit 48) to Week 24 (Visit 56) in Schedule 2. Ideally, these additional visits will be conducted weekly. These additional visits will be treated as interim visits (for more details, see the HVTN 805/HPTN 093 SSP).

After the Week 24 visit in Schedule 2, the ART re-initiation criterion is:

- Confirmed viral load ≥ 200 copies/mL (ie, on 2 consecutive samples).

A confirmatory sample should be drawn at the next visit (within approximately 1-2 weeks) following the first VL result ≥ 200 copies/mL (see HVTN 805/HPTN 093 SSP for details).

The above virologic ART re-initiation criteria are shown schematically in [Figure 3-1](#).

Figure 3-1 Virologic criteria for transition from Schedule 2 to Schedule 3 (ie, ART re-initiation)

In addition, at any time during Schedule 2, any of the following non-virologic criteria will trigger prompt ART re-initiation and transition to Schedule 3, *Follow-up on ART*:

- Confirmed CD4+ T-cell count < 350 cells/mm³ (ie, on 2 consecutive samples)
- Any HIV-related syndrome (eg, ARS, an opportunistic infection)
- Pregnancy or breastfeeding
- ART re-initiation requested by participant
- ART re-initiation requested by primary HIV care provider or CRS IoR (eg, if deemed medically necessary).

A confirmatory sample should be drawn at the next visit (within approximately 1-2 weeks) following the first CD4+ T-cell count < 350 cells/mm³ (see HVTN 805/HPTN 093 SSP for details).

3.3.4 Participants who decline to re-initiate ART

When ART re-initiation criteria are met, CRS staff will strongly recommend that the participant restart ART. Participants who decline to do so should be urged to continue clinic visits per the schedule they are in at that time (eg, Schedule 1 or Schedule 2) until such time as the participant re-initiates ART, at which time they should transition to Schedule 3. Monitoring such participants may require additional visits. Ideally, these visits will be conducted weekly. These additional visits will be treated as interim visits. For details, see the HVTN 805/HPTN 093 SSP.

4 Statistical considerations

4.1 Estimated accrual

Recruitment will target participants who received VRC01 or placebo and became HIV-infected during participation in HVTN 703/HPTN 081.

We calculate the expected trial size under different scenarios for the percentage of enrolled participants out of the total number of endpoint infected cases from HVTN 703/HPTN 081; scenarios include 25%, 50%, and 75%. Given an assumption of a common prevention efficacy at each dose (PE10 and PE30), the expected trial size will depend on different levels of PE. Under the null hypothesis (PE10 = PE30 = 0%), the total expected number of endpoint infections among placebo recipients is 26 and VRC01 recipients is 54 (Table 4-3 in the parent protocol HVTN 703/HPTN 081); therefore, we assume a trial size of 7, 13, or 20 placebo recipients and 14, 27, or 41 VRC01 recipients depending on the enrollment ratio. Under the alternative hypothesis (PE10 = PE30 = 60%), the total expected number of endpoint infections among placebo recipients is 35 and VRC01 recipients is 28 (Table 4-3 in the parent protocol); therefore, under the different enrollment ratio scenarios, we assume a trial size of 9, 18, or 26 placebo recipients and 7, 14, or 21 VRC01 recipients. These 6 sample size scenarios represent estimated upper and lower bounds for sample size given the expected number of endpoint infections under the null and alternative hypotheses respectively, as well as various scenarios for the percentage of eligible participants who will ultimately enroll in HVTN 805/HPTN 093.

4.1.1 Power to evaluate time to ART re-initiation criteria

Using data from the placebo arm of a therapeutic vaccine study which enrolled early treated patients (21), we modeled the time T (in weeks) to meet re-initiation criteria as a Weibull distribution with survival function $P(T > t) = \exp[-(\lambda t)^p]$, where $\lambda = \exp(-2.932) = 0.053$ and $p = 2.014$. From these parameters, we estimated the median time to meet re-initiation criteria as 15.6 weeks in the AMP placebo recipients. We can express the treatment effect in terms of either the HR θ or the factor β by which treatment increases the median time to meet re-initiation criteria; β and θ are related by $\beta = \theta^{1/p}$.

We model censoring of time to restart criteria using an exponential model and a maximum follow-up time of 72 weeks, where follow-up is censored at a rate of 20% per year due to either study termination or re-initiation of ART before reaching the restart criteria. Power for a 40%, 50%, 60%, and 70% reduction in hazard under different prevention efficacy scenarios are shown in [Table 4-1](#). These hazard reductions correspond to 29%, 41%, 58%, and 82% increases in the median time to meet restart criteria. Therefore, if VRC01 increases the median time to restart criteria 58% and the enrollment rate is 50%, then under the parent

study null hypothesis power to detect a difference in time to restart criteria is 72% while under the alternative hypothesis power is 62%.

Table 4-1 Power under different prevention efficacy results, different enrollment rates and different treatment effects, expressed as either reduction in hazard or percent increase in median time to meet re-initiation criteria

Enrollment Rate		Null hypothesis			Alternative hypothesis			
		25%	50%	75%	25%	50%	75%	
Expected number of placebos		7	13	20	9	18	26	
Expected number of VRC01		14	27	41	7	14	21	
Reduction in hazard	% Increase in median time to meet re-initiation criteria							
	40%	29%	20%	31%	44%	16%	27%	36%
	50%	41%	31%	49%	67%	23%	42%	57%
	60%	58%	46%	72%	89%	35%	62%	81%
	70%	82%	65%	90%	98%	52%	85%	95%

4.1.2 Sample size considerations for safety

The goal of the safety evaluation for this study is to identify safety concerns associated with ATI. The ability of the study to detect SAEs (see Section 4.2.3.1) can be expressed by the true event rate above which at least 1 SAE would likely be observed and the true event rate below which no events would likely be observed. Under the enrollment rate and PE scenarios described in Section 4.1, Table 4-2 shows the true event rate such that there is a 90% chance of observing at least 1 event (or no events) among three groups; 1) the placebo recipients only, 2) the VRC01 recipients only, or 3) all enrolled participants.

Table 4-2 True event rates above which at least 1 SAE (or below which no events) would likely be observed in a group of size *n* participants. Event rates are computed separately for various values of *n* given by the range and midpoint for the estimated number of participants among 3 groups; 1) the placebo recipients only, 2) the VRC01 recipients only, or 3) all enrolled participant based on the enrollment scenarios described in Section 4.1.

n	Placebo recipients			VRC01 recipients			All enrolled		
	7	17	26	7	24	41	16	39	61
At least 1 event	28.0%	12.7%	8.5%	28.0%	9.1%	5.5%	13.4%	5.7%	3.7%
No events	1.5%	0.6%	0.4%	1.5%	0.4%	0.3%	0.7%	0.3%	0.2%

4.2 Statistical analyses

Analyses for primary endpoints will be performed using SAS and R. All other descriptive and inferential statistical analyses will be performed using SAS, StatXact, or R statistical software.

No formal multiple comparison adjustments will be employed for multiple safety endpoints or secondary endpoints. However, multiplicity adjustments will be made for certain laboratory assays, as discussed below, when the assay endpoint is viewed as a collection of hypotheses (eg, testing multiple peptide pools to determine a positive response).

4.2.1 Analysis variables

The analysis variables consist of baseline participant characteristics, safety, and laboratory outcomes for primary- and secondary-objective analyses.

4.2.2 Baseline comparability

Groups defined by the parent protocol treatment arms will be compared for baseline participant characteristics using descriptive statistics.

4.2.3 Primary virologic analysis

In this study we either compare placebo recipients from HVTN 703/HPTN 081 with historical controls (ie, SPARTAC cohorts described in Gossez et al (1)) or we condition on HIV-infection with the intention of comparing virologic outcomes by randomized treatment assignment from HVTN 703/HPTN 081.

When comparing outcomes by treatment assignment among infected AMP participants, we are conditioning on a postrandomization event, HIV-infection. Consequently, a two-sample test for a difference in outcome is subject to postrandomization selection bias. A direct comparison of virologic outcomes between treatment groups, which measures the “net treatment effect,” does not have a causal interpretation (114). As an example of the type of bias that can occur, suppose VRC01 protects against mild viruses but is not effective against virulent viruses. If this were true, we might see longer time to re-initiation criteria in VRC01 recipients than placebo recipients whereas, if we restricted only to those participants infected with a virulent HIV strain, we might see shorter time to re-initiation criteria in the VRC01 group. Therefore, a two-sample test comparing time to re-initiation criteria between treatment groups could give a misleading impression that VRC01 shortens viral suppression time during ATI while the causal interpretation of this hypothetical example would be that for virulent viruses, VRC01 increases viral suppression time during ATI compared to placebo.

Approaches will be taken to ensure robust and unbiased results. Implementation of targeted minimum loss-based estimation (TMLE) methods, used to address the objectives in the following sections, will be fully prespecified in the statistical analysis plan (SAP) to ensure objective and reproducible inference.

When comparing by treatment assignment among AMP cases, each analysis will be done pooling the VRC01 recipients versus placebo recipients with

supplemental analyses done separately for each dose group versus the placebo recipients.

4.2.3.1 Time to ART re-initiation criteria

The primary outcome is the time from the start of treatment interruption until the participant meets criteria to re-initiate ART.

For a comparison of the placebo group to historical controls a Cox proportional hazards model with the indicator of AMP placebo group versus historical control group will be used to estimate the cumulative incidence in each group, as well as the HR, all with 95% confidence intervals and associated 2-sided p-values, where the model controls for baseline covariates thought to potentially predict both HIV-1 infection and the instantaneous hazard of meeting the ART re-initiation criteria. This is needed for controlling for potential selection bias given that analyzed treatment groups are not randomized. Plots of the estimated cumulative incidence will be shown by treatment group.

A Cox proportional hazards model with the indicator of assignment to a mAb group versus the control group will be used to estimate the cumulative incidence in each of the infected VRC01 and infected placebo groups, as well as the HR, all with 95% confidence intervals and associated 2-sided p-values, where the model controls for baseline covariates thought to potentially predict both HIV-1 infection and the instantaneous hazard of meeting the ART re-initiation criteria. This is needed for controlling for potential postrandomization selection bias given that analyzed treatment groups are selected postrandomization. Plots of the estimated cumulative incidence will be shown by treatment group.

As a supportive analysis of this hypothesis, TMLE may be used to estimate cumulative incidences of the primary efficacy endpoint over time for the pooled mAb arm and the control arm. Iterative mean-based TMLE is used for this analysis as described by Benkeser et al (115). The Super Learner (116) is used to generate initial estimates of the conditional censoring distribution and the iterated conditional means. This analysis will use TMLE as implemented in the R package `survtmle` available on CRAN (117).

4.2.3.2 Frequency of sustained post-treatment HIV control

The same covariate adjusted model used to estimate cumulative incidence of meeting the re-initiation criteria for ART over time, described in the previous section, will be used to compare the rates of failure to maintain HIV control at 24 weeks between the placebo group and historical controls and between the 2 treatment groups.

4.2.4 Secondary analyses of immune responses, reservoir measurements and viral load

Analyses of immune responses and reservoir measurements will be descriptive using appropriate plotting techniques for describing measurements at a fixed time point (eg, boxplots and barplots) or longitudinally (eg, spaghetti plots) separately by treatment group. In addition, if enough samples are assayed we plan to do inferential and descriptive analyses as described in the following sections.

4.2.4.1 Evaluate the difference in anti-HIV immune responses or reservoir size between VRC01 and placebo recipients

TMLE will be used to estimate mean endpoints in each of the infected VRC01 and infected placebo groups, as well as the mean difference, all with 95% confidence intervals and associated 2-sided p-values, where the TMLE controls for all baseline covariates thought to potentially predict both HIV-1 infection and one of the secondary endpoints under study. This is needed for controlling for potential postrandomization selection bias given that analyzed treatment groups are selected postrandomization.

4.2.4.2 Assess whether anti-HIV immune responses or reservoir size are associated with time to meeting ART re-initiation criteria

Cox regression will be used to estimate cumulative incidence over time for groups defined by levels of immune response or reservoir size for each treatment group.

4.2.4.3 Time to viral load > 200

Secondary endpoint 2 is time until the participant has a viral load > 200. The same methodology used to assess time to ART re-initiation criteria will be used for this endpoint. In this analysis we will compare cumulative incidence at week 8 in each of the infected VRC01 and infected placebo groups supplemented by a sensitivity analysis based on cumulative incidence at weeks 8, 16, and 24.

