3.2.2 Secondary objectives and endpoints

Secondary objective 1

- To evaluate the effect of early ART initiation, with or without having received VRC01 in the immediate pre-HIV acquisition period and/or during early infection on the development of anti-HIV immune responses and on the potential association of those immune responses with time to meeting criteria for ART re-initiation in participants undergoing ATI

Secondary endpoints 1

- Response rate, magnitude, and polyfunctionality of HIV-specific CD4+ and CD8+ T-cell responses as measured by flow cytometry
- Magnitude and breadth of neutralizing antibody (nAb) responses against autologous and heterologous HIV isolates, as measured by TZM-bl neutralization assay
- Non-neutralizing, Fc γ R-mediated antibody effector functions such as antibody-dependent cellular cytotoxicity (ADCC), antibody-dependent cellular phagocytosis (ADCP), and virion capture
- Frequency of dendritic cell activation and maturation markers, as measured by flow cytometry or other cell phenotyping assays
- Frequency of T- and B-cell activation and exhaustion markers, as measured by flow cytometry or other cell phenotyping assays

Secondary objective 2

- To evaluate the effect of early ART initiation, with or without having received VRC01 in the immediate pre-HIV acquisition period and/or during early infection on viral load in participants undergoing ATI

Secondary endpoint 2

- Cumulative incidence of participants with viral load ≥ 200 at weeks 8, 16, and 24

Secondary objective 3

- To evaluate the effect of early ART initiation, with or without having received VRC01 in the immediate pre-HIV acquisition period and/or during early infection on HIV reservoir size before and after ATI, and whether HIV reservoir measurements are associated with time to meeting criteria for ART re-initiation in participants undergoing ATI

Secondary endpoint 3

- Frequency of CD4+ T cells carrying intact and/or total pro-viral HIV DNA, replication competent virus, and/or cell-associated HIV RNA

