8.2 Assay timepoints

Endpoint assays for immunologic and virologic responses will be performed on a subset of participants to be determined by the outcome of primary objectives and endpoints.

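### The marker-to-outcome analysis is planned only by marker level within each arm; for quantitative markers, an arm-stratified Cox model on the continuous marker, reported with arm-specific slopes and a joint test, would use the small sample better

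*Protocol*

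**What the plan says.** The association between markers and outcome belongs to secondary objectives 1 and 3. Objective 1 asks, among other things, "on the potential association of those immune responses with time to meeting criteria for ART re-initiation in participants undergoing ATI"; objective 3 asks the same of reservoir measurements (Protocol 3.2.2).

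The whole planned method is one sentence in Protocol 4.2.4.2: a Cox regression is to give cumulative incidence curves "for groups defined by levels of immune response or reservoir size for each treatment group". SAP 6.4 repeats it without further detail. Neither document gives the number of levels, the cut-points, the marker timepoint, a test, a model across arms or a marker-by-arm interaction.

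Two other passages limit the analysis. Protocol 4.2.4 is descriptive by default and adds that "if enough samples are assayed we plan to do inferential and descriptive analyses as described in the following sections". Protocol 8.2 says "Endpoint assays for immunologic and virologic responses will be performed on a subset of participants to be determined by the outcome of" the primary analyses.

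On arm sizes, Protocol 4.1 says "we assume a trial size of 7, 13, or 20 placebo recipients and 14, 27, or 41 VRC01 recipients" under the parent trial's null hypothesis and "we assume a trial size of 9, 18, or 26 placebo recipients and 7, 14, or 21 VRC01 recipients" under its alternative. Neither document states power for the marker analysis.

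**The concern.** Finding biomarkers that predict control is one of the stated reasons for interrupting treatment (Protocol 1.1 and 2.5). Most of the markers are quantitative: percentages of responding T cells (8.3.1), neutralization magnitude (3.2.2) and reservoir quantity (8.6). Grouping such a marker discards the ordering within each group. Examining each arm alone then discards the information the arms share when the marker works the same way in both. With samples this small, both losses matter.

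Because levels and cut-points are open, they could also be chosen after the data are seen. Curves by level do not by themselves give an association estimate with a confidence interval.

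**Working it through.** **1. Reproduce the plan's model.** Protocol 4.1.1 uses S(t) = exp[-(λt)^p] with λ = exp(-2.932) and p = 2.014, exponential censoring at 20% per year and a 72-week cap. The median is (ln 2)^(1/p)/λ = 0.8336 × 18.765 = 15.64 weeks (stated 15.6). Simulating the arm comparison at HR 0.40 and 50% enrollment gives 71.8% (stated 72%) and 64.0% (stated 62%). All 24 cells of Protocol Table 4-1 reproduce within 2 points.

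**2. Cell sizes, assuming a median split within arm and everyone assayed.**
- 25% enrollment: 7/2 = 3.5 to 14/2 = 7.
- 50% enrollment: 13/2 = 6.5 to 27/2 = 13.5.
- 75% enrollment: 20/2 = 10 to 41/2 = 20.5.

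**3. Power when the marker effect is shared by both arms.** Assumptions not in the documents: standard-normal marker, HR per SD of 1.5 or 2.0, no arm effect, two-sided 5%. There were 20,000 trials per row, censoring at -ln(0.8)/52 per week. In arm a, let U_a = Σ(x - mean of x at risk) and V_a = Σ(variance of x at risk), summed over events.
- Split: U_a²/V_a on 1 df, with x the above-median indicator in one arm (a log-rank test).
- Common slope: (U_0 + U_1)²/(V_0 + V_1) on 1 df, with x continuous and stratified by arm.
- Joint test: U_0²/V_0 + U_1²/V_1 on 2 df, i.e. marker plus interaction.

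| Placebo/VRC01 | HR per SD | Split, placebo | Split, VRC01 | Common slope | Joint | Common slope ÷ larger arm's split |
|---|---|---|---|---|---|---|
| 7/14 | 1.5 | 0.12 | 0.18 | 0.31 | 0.24 | 1.7 |
| 13/27 | 1.5 | 0.16 | 0.31 | 0.59 | 0.48 | 1.9 |
| 20/41 | 1.5 | 0.24 | 0.44 | 0.78 | 0.69 | 1.8 |
| 9/7 | 1.5 | 0.13 | 0.12 | 0.23 | 0.18 | 1.8 |
| 18/14 | 1.5 | 0.21 | 0.18 | 0.47 | 0.37 | 2.2 |
| 26/21 | 1.5 | 0.30 | 0.25 | 0.66 | 0.56 | 2.2 |
| 7/14 | 2.0 | 0.17 | 0.34 | 0.65 | 0.53 | 1.9 |
| 13/27 | 2.0 | 0.31 | 0.62 | 0.94 | 0.89 | 1.5 |
| 20/41 | 2.0 | 0.48 | 0.81 | 0.99 | 0.98 | 1.2 |
| 9/7 | 2.0 | 0.21 | 0.17 | 0.49 | 0.37 | 2.4 |
| 18/14 | 2.0 | 0.44 | 0.34 | 0.86 | 0.78 | 1.9 |
| 26/21 | 2.0 | 0.60 | 0.50 | 0.96 | 0.93 | 1.6 |

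Ratios use unrounded values. In the smallest odd-sized arms they also depend on which side of the split the middle person falls.

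Both steps contribute. In a 3,000-trial run at 13/27 and HR 1.5, power was 0.32 for the VRC01 split, 0.46 for the continuous marker in VRC01 alone, 0.42 for an arm-stratified split and 0.59 for the common slope.

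**4. False positives with no marker effect.** Across the six size scenarios the common slope rejects in 5-6% of trials, the joint test in 6-7% and a single within-arm split in 6-9%. Declaring a finding when either arm's split has p < 0.05 gives 12-17%. The splits' power above is therefore slightly flattered.

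**5. Power when the effect is not shared (HR 2.0 per SD).**

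| Setting | Split | Common slope | Joint | Continuous, VRC01 only |
|---|---|---|---|---|
| VRC01 only, 13/27 | 0.61 (VRC01) | 0.63 | 0.74 | 0.82 |
| VRC01 only, 18/14 | 0.34 (VRC01) | 0.23 | 0.40 | 0.51 |
| VRC01 only, 26/21 | 0.50 (VRC01) | 0.33 | 0.60 | 0.71 |
| Opposite directions, 18/14 | 0.49 (either arm, Bonferroni) | 0.07 | 0.78 | 0.51 |

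**6. Can the interaction test protect the common slope?** With HR 1.75 per SD in VRC01 and none in placebo (3,000 trials), its power is 0.13 (7/14), 0.24 (18/14), 0.28 (13/27), 0.34 (26/21) and 0.40 (20/41). At HR 2.0 it is 0.18 to 0.56. It would usually miss the difference.

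**7. Threshold-shaped effect.** With a high/low HR of 2.25 at 13/27 (3,000 trials), power is 0.40 for the common slope, 0.46 for an arm-stratified median split and 0.37 for the VRC01 split.

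**The case against.** A reader might infer that one pooled continuous model roughly doubles power at no cost. The documents do not support that. They give no marker effect size, number of levels or test, so any multiple belongs to an assumed comparator. Nor is pooling free: step 5 shows the common slope losing to the VRC01 split when only that arm carries the effect, and failing when directions differ. Arm-specific associations are plausible here, because the secondary hypotheses (Protocol 3.1.2) say VRC01 alters immune responses and the reservoir. Estimating by treatment group is therefore a defensible aim.

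It is also fair to say that the plan describes estimation rather than a test, does not state that separate models will be fitted by arm, and claims no power. The study is exploratory, and inference on this question is secondary and conditional on enough assays. Not every marker is continuous: response rate is an endpoint, and reservoir values may fall below detection.

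All of this stands. It argues against relying on the common slope alone, and does not rescue grouping as the only analysis. Under log-linear effects, the continuous marker within VRC01 beats the VRC01 split when only that arm carries the effect (0.51 against 0.34 at 18/14). The joint test also beats the splits there and when directions are opposite.

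**Conclusion.** The point holds as an inexpensive improvement to a secondary analysis; the plan contains no false power claim. For quantitative markers, analysis by level within arm gives up power at every planned size when the effect is log-linear and shared. At HR 1.5 to 2.0 per SD the common-slope test has about 1.2 to 2.4 times the power of the larger arm's median split. The low end is 20/41 at HR 2.0, where that split already reaches 81%; elsewhere the ratio is at least 1.5. The joint test keeps much of the gain and does not depend on a shared slope.

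These figures assume a median split, a log-linear effect and everyone assayed. Cells of only a few people describe the smaller scenarios and do not describe 75% enrollment. A reader might also infer that the change would make a null result informative. It often would not: at HR 1.5 the common slope has only 23% to 59% power at 25-50% enrollment.

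**What to change.** In Protocol 4.2.4.2 and SAP 6.4:

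- For quantitative markers, make the inferential analysis a Cox model stratified by treatment arm, with the log10 marker as a continuous covariate and an arm-by-marker interaction.
- Report the 2-df joint test, the arm-specific HRs per SD with 95% CIs, and the common-slope HR. Do not use the interaction p-value to decide whether the common slope is adequate.
- Keep the level-group curves as display, with the number of levels and cut-points fixed in advance.
- State the marker timepoint and a rule for values below detection. Keep binary response endpoints categorical.

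The cost is wording only, with no new data or visits. The statistical price is the log-linearity assumption, under which a threshold-shaped marker may be better served by grouping, and some power given up by the joint test relative to the common slope when the effect truly is shared (13/27, HR 1.5: 0.48 against 0.59).
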